7.2 Statistical Methods

To examine the moderating effects of the *GRIK1* SNP rs2832407 on the response to TOP (Specific Aim 1.)

CONFIDENTIAL

The four medication (Topiramate/Placebo) by *GRIK1* genotype (CC vs. AA/AC) groups will be compared on the weekly number of heavy drinking days using mixed effects models for count responses (83, 84), fitted using PROC GLIMMIX in SAS and the HGLM module of the HLM7 program. Estimates of effects over the final six weeks from the models, with associated standard errors and confidence intervals, will be used to test the primary hypothesis, i.e., medication group by genotype contrasts within the final six weeks will directly address the significance and pattern of differences in distributions of HDDs among the four medication by genotype groups.

The fixed effects for the primary models will include binary factors for intervention group (Topiramate/ Placebo) and *GRIK1* genotype (CC or AA/AC), and their interaction, with covariates for linear and quadratic time trends and further terms for group by time, genotype by time, etc., as appropriate for model fit. The random effects will include a random intercept and, if necessary, residual autocorrelations, random slopes, or other specifications will be used (Molenberghs, Verbeke et al. 2005, McCulloch, Searle et al. 2008). Although the primary contrasts will concentrate on the final six weeks, these models utilize all available data from all subjects, so the analyses follow the intent-to-treat principle. If the polynomial time trends described above do not capture the range of individual trajectories observed in the trial, then more flexible non-linear time trends can also be fitted. Additional covariates can also be included in the models, allowing for sensitivity analyses for effects of covariate imbalances, and to examine moderation effects (see below) and group by goal of treatment (reduced drinking or abstinence) interactions. For example, we will also include the proportion of European ancestry as a covariate, to adjust for admixture. Here, AIMs genotype data will be used to calculate ancestry proportions using a principal components method implemented in EIGENSTRAT (Price, Patterson et al. 2006) or PLINK (Purcell, Neale et al. 2007), and the proportion will be included in the model as a covariate. The models can also be extended to allow for zero inflation, where weekly patterns of abstinence may yield more zero counts of heavy drinking days than can be accommodated by a Poisson model.

To examine the relations among daily process measures of expectancies, medication use, and drinking level (Specific Aim 2.)

Multilevel models similar to those described above will be used to evaluate the associations between alcohol expectancies and daily drinking and how these associations vary as a function of medication group and rs2832407 genotype. Similar to Kranzler et al. (2013), we will focus on predicting nighttime drinking (i.e., drinks consumed after the early evening report), but here we will use alcohol-related expectancies reported during the early evening in the daily survey. Nighttime drinking levels will be determined by subtracting the number of drinks consumed during the current day from the total number of drinks consumed for that day (reported the following day). We will follow the general analysis scheme used by Kranzler, Armeli et al (2013), but will use mixed effects/multilevel models, rather than generalized estimating equations (GEE) models (Walls, Jung et al. 2006, Schafer 2006). We will examine the number of drinks consumed (using a Poisson model). We will use the HGLM module of the HLM7 program, as it is more flexible for some of our models than PROC GLIMMIX in SAS. Analysis will focus on the last six weeks of treatment, consistent with the analyses of the primary outcome in Specific Aim 1.

Predictors in these models will include 6 day-of-the-week contrasts in the level-1 model (i.e., including responses that change over days within person), to control for day of the week trending in the outcomes [e.g., greater propensity to drink on weekends (Armeli, Carney et al. 2000, Armeli, Tennen et al. 2000)], along with linear and quadratic study time contrasts and daytime drinking. The day-level predictor of interest (i.e., expectation of positive effects of drinking) will also be included in the level-1 portion of the model. The outcome expectancy

CONFIDENTIAL

predictor will be person-mean centered (91). The level-2 portion of the model (i.e., measures that do not change over days) will include treatment group, binary factors for rs2832407 genotype (i.e., CC vs. A-carrier) and associated interaction terms. This analysis will test the hypothesis that TOP will significantly reduce positive alcohol expectancies relative to PLA, but only in C-allele homozygotes, similar to the analysis of the primary outcome in Specific Aim 1.

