Our primary hypothesis is that the effect will be significantly larger in rs2832407 C-allele homozygotes than in A-allele carriers. We will also examine the SNP's moderating effects on the efficacy of topiramate in improving other self-reported drinking measures (e.g., abstinent days), adverse consequences of drinking (e.g., the Short Index of Problems score: SIP; see section 6.8.3 below), and biological measures of heavy drinking (e.g., %dCDT, an improved assay for carbohydrate deficient transferrin). Finally, we will conduct 3- and 6-month post-treatment assessments on the hypothesis that rs2832407 C-allele homozygotes will show greater reduction in primary and secondary outcomes after the medication is discontinued.

The primary outcome for the study is the frequency of heavy drinking (defined as 4 or more drinks in a day for women and five or more drinks in a day for men).

Secondary outcomes include the number of abstinent days, absence of any heavy drinking days during the last month of treatment, mean daily alcohol consumption, drinks/drinking day, %dCDT and gamma glutamyl transpeptidase (GGTP) levels, and severity of alcohol-related problems (i.e., SIP score), using models similar to those described below for the primary outcome.

2.2. Secondary Objective: To examine daily processes, including expectancies regarding the positive effects of drinking and confidence in resisting heavy drinking and their interaction with genotype and medication group to predict the intensity of nighttime drinking. We expect that evening reports of a high level of positive expectations regarding alcohol's effects and a low level of confidence in resisting heavy drinking will be associated with heavier drinking later that night.

Our secondary hypotheses are that topiramate treatment will significantly reduce both positive alcohol-outcome expectancies and confidence in resisting heavy drinking across the weeks of the study and nighttime drinking measured daily in rs2832407 C-allele homozygotes, but not A-allele carriers.

2.3 Optional MRI Sub-Study Objective: Conduct an optional sub-study to examine the effects of topiramate on resting baseline (RB) cerebral blood flow and alcohol cue reactivity using functional magnetic resonance imaging (fMRI). The goals, rationale, background and study methods for this objective are described in Appendix I: "Brain Mechanisms of Topiramate's Effects on Heavy Drinking."

3 Study Design

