6.3 Visit 1 (Week 1; Baseline and First Treatment Visits)

Subjects will be informed of their eligibility status within 5 days and scheduled for a baseline assessment within 30 days of the screening visit. All subjects not eligible for the study will be referred to the appropriate treatment center or other research study. Eligible subjects will undergo a **baseline** research evaluation (lasting up to 2 hours) within 30 days of completing the screening visit.

Subjects will be asked to complete a breathalyzer test. If a subject's breath alcohol concentration is $\geq 0.02\%$, an investigator will evaluate whether the subject is too impaired to complete the study assessments. The study visit may be completed at the discretion of the investigator. If the subject is deemed to be unable to complete assessments, the investigator may ask the subject to wait until his or her blood alcohol level decreases or if that is not feasible to return the next day after having consumed no alcohol. Prior to discharge from the TRC, a clinician will assess the subject to ensure that it is safe for the subject to leave. Study staff will complete the following assessments with all subjects (the exception being that only for women of childbearing potential, will study staff obtain a urine sample for a pregnancy test).

- The Patient Health Questionnaire (PHQ-9), a validated 9-item self-report measure of depressive symptoms that yields a total score of 0-27 (Kroenke, Spitzer et al. 2001), will be administered at each visit.
- The International Neuropsychiatric Interview 6.0 (Mini 6): Suicidal risk will be assessed using the MINI Suicidality section (B) at each study visit and, if rated greater or equal to 9 (i.e., clinically significant suicidal ideation), the physician will be consulted to decide on the appropriate clinical management.
- Daily Interactive Voice Response (IVR) Telephone Call (daily for 12 weeks, beginning with the initiation of treatment)

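### The Aim 2 analysis specifies no test of the course of expectancies and confidence over the study that section 2.2 hypothesises, and has neither as an outcome

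*Combined protocol and SAP*

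**What the plan says.** **Hypothesis (section 2.2).** The prediction for this aim reads: "topiramate treatment will significantly reduce both positive alcohol-outcome expectancies and confidence in resisting heavy drinking across the weeks of the study". A fall in nighttime drinking, measured daily, is predicted as well. Both are expected in C-allele homozygotes but not in A-allele carriers.

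**Data (section 6.3).** The telephone diary runs "daily for 12 weeks, beginning with the initiation of treatment". That is 84 days, with no daily reports before treatment.

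**Analysis (section 7.2, Specific Aim 2).**
- Window: "Analysis will focus on the last six weeks of treatment, consistent with the analyses of the primary outcome in Specific Aim 1".
- Models: "Multilevel models similar to those described above will be used to evaluate the associations between alcohol expectancies and daily drinking".
- Outcome: nighttime drinking, as a drink count in a Poisson model.
- Time: it enters the level-1 list beside the day-of-week contrasts, "along with linear and quadratic study time contrasts and daytime drinking".
- Expectancy: "The day-level predictor of interest (i.e., expectation of positive effects of drinking) will also be included in the level-1 portion of the model". It is person-mean centred.
- Level 2: treatment, genotype and their associated interactions, not itemised further.

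The section closes by saying that this analysis will test whether topiramate reduces expectancies relative to placebo in C-allele homozygotes only.

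**Aim 1, for comparison (section 7.2).** "Although the primary contrasts will concentrate on the final six weeks, these models utilize all available data from all subjects". Group-by-time and genotype-by-time terms are named there, to be used as model fit requires.

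**Size (section 7.1).** About 15,000 person-days are expected at about 20% missing. The adequacy benchmark is 30 subjects with 30 observations each.

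**The concern.** The hypothesis concerns two diary ratings and how they move over the study. The analysis concerns a third variable, drinks after the evening report, with its focus on the second half of treatment.

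The early weeks matter for the course. Table 1 reaches the maximal daily amount in week 6. Section 1.4 reports an open-label trial with less drinking and craving by week 2, a controlled trial whose arms began to separate after the first month, and a predecessor trial with a medication-by-week interaction on heavy drinking days. Because the diary starts with treatment, weeks 1–6 are also the only daily reference against which later change in expectancy or confidence can be seen.

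At stake is whether the trial can report on its stated secondary hypothesis. Someone following section 7.2 would obtain the association between expectancy and later drinking and how it varies by arm and genotype. They would not obtain an effect of topiramate on expectancy or confidence, or a comparison of courses. Section 7.2 also leaves open whether weeks 1–6 enter the fit, so two analysts could use different data sets.

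**Working it through.** **1. Hypothesis against model**

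| Element of section 2.2 | What section 7.2 provides for Aim 2 |
|---|---|
| Reduction in positive expectancies | Expectancy is a level-1 predictor; no model has it as the outcome |
| Reduction in confidence | Not in the model described (section 3.2.2 mentions self-efficacy, but as a correlate of drinking) |
| Nighttime drinking measured daily | Is the outcome |
| Course over the study weeks | Linear and quadratic time as covariates; no medication × genotype × time term or contrast named |
| C-allele homozygotes only | Treatment, genotype and associated interactions at level 2 |

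Person-mean centring subtracts each subject's own average, so the centred predictor averages zero in every subject and hence in every arm. A difference between arms in average expectancy is removed before the model is fitted. The coefficients then describe how day-to-day departures in expectancy relate to drinking that night. They cannot show that topiramate lowered expectancy.

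**2. The plan's person-day figure**

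Inputs: 200 randomized (Study Summary); 84 days (12 weeks, section 6.3); about 20% missing (section 7.1). Person-days = subjects × days × proportion observed.

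- Full diary: 200 × 84 × 0.80 = 13,440. This is 13,440 / 15,000 = 89.6% of the stated figure, so the figure does not reproduce.
- Full diary, 188 subjects (the Aim 1 power base): 188 × 84 × 0.80 = 12,634.
- Diary plus 6-day taper: 200 × 90 × 0.80 = 14,400.
- Getting close to 15,000 needs an input the plan does not state for the diary: about 10% missing (200 × 84 × 0.90 = 15,120), or 91 days (200 × 91 × 0.80 = 14,560).

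**3. What the figure says about the window**

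- Weeks 7–12, no missing reports: 200 × 42 = 8,400.
- Weeks 7–12, 20% missing: 200 × 42 × 0.80 = 6,720, or 6,720 / 13,440 = 50% of the full diary.

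Even a complete six-week diary falls well short of 15,000, so the power statement presupposes the full treatment period.

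**4. The plan's own benchmark**

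30 × 30 = 900 person-days. A strict six-week window would give 200 subjects with 42 × 0.80 = 33.6 reports each, which exceeds the benchmark in subjects, in reports per subject and in total. The plan does not show that the benchmark applies to medication × genotype moderation of a daily slope.

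**The case against.** The strongest defence is that the window is deliberate and harmless. It matches the primary objective and covers the weeks after titration. In a randomized comparison, a weeks 7–12 difference between arms can show a reduction relative to placebo without a pre-treatment diary. The phrase about the study weeks can be read simply as during the study. The models are called similar to those of Aim 1, where time interactions are allowed. All of this stands as far as the level in weeks 7–12 goes. It does not supply a comparison of courses, because Aim 2 names none, and it does not make expectancy or confidence an outcome.

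A reader might go further and infer that half the diary is discarded. On that view standard errors for within-person terms rise by √2 = 1.41, and a term with 80% power falls to about 51%: (1.96 + 0.84) / 1.41 = 1.98, barely above 1.96. The documents do not support this. The text speaks of focus, not exclusion; it ties itself to an analysis that uses all available data; and the person-day count fits only the full period. The calculation also assumes that information is proportional to days and that power starts at exactly 80%. Between-subject variation in slopes limits any such loss, and the number of subjects is unchanged.

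A reader might also infer that any divergence arising during titration is missed. One that arises then and persists would still appear as a difference in weeks 7–12. Only a transient effect, or the shape of the course, would be lost.

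**Conclusion.** The concern holds in a limited form. Aim 2 as written does not test the hypothesised course, because no medication × genotype × time contrast is named; this is so even if all 84 days are modelled. The closing claim in section 7.2 that the analysis tests a reduction in expectancies is not met by a model in which expectancy is a centred predictor. The same gap applies to confidence. Nighttime drinking is an outcome, so a contrast of its level in weeks 7–12 is possible.

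No loss of data or power is shown. If the restriction were strict, 6,720 of 13,440 person-days would remain, assuming 200 subjects and 20% missing. The stated 15,000 should be corrected in either case. These counts are of daily reports; nighttime drinking also needs the next day's report, so usable days for that outcome may be fewer.

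This is a cheap improvement to a secondary aim and does not affect the primary analysis.

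**What to change.** Amend section 7.2 (Aim 2) and section 7.1:

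1. State that the Aim 2 models are fitted to all 84 daily reports.
2. Specify three models, with positive expectancy, confidence in resisting heavy drinking, and nighttime drinking each as the outcome. Each should include medication × genotype × linear and quadratic time, with the lower-order terms. The Poisson model is stated for drink counts, so name a suitable distribution for the 5-point ratings.
3. Pre-specify two results per outcome: the medication × genotype difference in course over weeks 1–12, and, from the same model, the weeks 7–12 contrast that matches Aim 1.
4. Keep the planned model of expectancy predicting nighttime drinking, described as a test of association and its moderation.
5. Restate the person-days as 13,440 on the stated inputs, or give the inputs behind 15,000.
6. Confirm the intended direction for confidence. Section 2.2 hypothesises a reduction, yet expects low confidence to go with heavier drinking.

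The cost is SAP wording, a few more model terms and 3 × 2 = 6 secondary results, which should be labelled as such. No new data are needed.

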16.4.2	Data Collection and Follow-up for Withdrawn Subjects	64
16.5	INFORMED CONSENT AND SCANNING VISIT 1 (APPROXIMATELY 3 HOURS).....	50
16.6	LABORATORY/MRI SESSION 2 VISIT (APPROXIMATELY 2 HOURS)	68
17	SUB-STUDY STATISTICAL PLAN	53
17.1	SAMPLE SIZE DETERMINATION	53
17.2	STATISTICAL METHODS.....	53
17.2.1	Imaging Data Processing	53
17.2.2	Imaging Data Analyses	68
17.2.3	Behavioral Analyses	54
17.3	SUBJECT STIPENDS OR PAYMENTS.....	54
18	CONFIDENTIALITY	58
19	APPENDIX II: CLINCARD PROGRAM: DATA SECURITY & PRIVACY STATEMENT.....	60
20	REFERENCES.....	61

List of Abbreviations

AD: Alcohol dependence
AUD: Alcohol use disorder
CDT: carbohydrate-deficient transferrin
%dCDT: percent disialotransferrin
DSM: Diagnostic and Statistical Manual of Mental Disorders
GGTP: gamma glutamyl transpeptidase
HDD: Heavy drinking day
SNP: single nucleotide polymorphism
TLFB: Timeline Follow-back Method

CONFIDENTIAL

This material is the property of the University of Pennsylvania. Do not disclose or use except as authorized in writing by the study sponsor

Study Summary

Title	A randomized, double-blind placebo-controlled pharmacogenetic study of topiramate in European-American heavy drinkers
Short Title	Topiramate by Genotype (TOP-G)
Protocol Number	
Phase	2
Methodology	Randomized, double-blind, placebo-controlled, parallel-groups
Study Duration	5 years
Study Center(s)	University of Pennsylvania and Corporal Michael J. Crescenz VA Medical Center (CMCVAMC)
Objectives	1) To examine the moderating effect of rs2832407 in GRIK1 on the efficacy of topiramate 200 mg/day in reducing the frequency of heavy drinking; 2) To examine daily processes, including expectancies regarding the positive effects of drinking and confidence in resisting heavy drinking, and their interaction with genotype and medication group to predict nighttime drinking; 3) To conduct 3- and 6-month post-treatment follow-up assessments to examine the persistence of treatment effects; 4) To conduct an optional sub-study to examine the effects of topiramate on resting baseline cerebral blood flow and alcohol cue reactivity using functional magnetic resonance imaging.
Number of Subjects	A total of 200 subjects will be randomized (up to 100 at the CMCVAMC site)

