7.1 Sample Size Determination

Power for the analysis for **Specific Aim 1**, as described below, will be determined by the patterns of outcomes in the final six weeks, so power estimates are based on weeks 7 through 12 as a 6-week trial, with adjustments for loss to attrition between baseline and week 6. Based on our prior study (Kranzler, Covault et al. 2014), we anticipate that, through the first six weeks, 94% of subjects (i.e., n=47 per group) will provide data, despite up to 10% discontinuing medication. We anticipate an additional 6% loss due to dropout from research during the final six weeks, also with 10% discontinuing treatment. In these power estimates, we use a square root transform to approximate the Poisson distributions by Normal distributions, on which we base our estimates using the methods of Hedeker et al. (1995) and Stroup (1999). Our primary comparison is the interaction effect of *GRIK1* with TOP. In our previous study, for the square root Poisson scale, we observed a standardized effect (Cohen 1988) of d=0.27 for TOP relative to PLA in the AA/AC group and a standardized effect of d=0.93 for TOP relative to PLA in the CC group. We have a single primary hypothesis, so we consider power for a two-sided test at $\alpha=0.05$, with a total of $4 \times 47=188$ subjects, with 6% research loss to attrition across six weeks. Finally, we assume a within-subject correlation of 0.35 for the repeated measures. With these assumptions, we have 81% power for the effects observed in our prior study. For **Specific Aim 2**, we used simulation studies (Kreft and De Leeuw 1998) to evaluate the adequacy of our sample size in relation to moderation by the CC genotype of TOP's effects on the contingent relation between early evening outcome expectancies and nighttime drinking (Kranzler, Armeli, et al. 2013). These show that designs having at least 30 level-2 units with 30 observations each (i.e., 900 total person days) will provide power of 80% to detect small effect sizes. Assuming a rate of missing data of about 20% (Kranzler, Armeli, et al. 2013), we will have approximately 15,000 person days for the comparison of TOP and PLA, which will provide high power to detect a small effect.

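### The Aim 2 model in Section 7.2 predicts nighttime drinks from person-mean-centred expectancy, so it does not test the hypothesis assigned to it, that topiramate lowers positive expectancies in C-allele homozygotes; no model has confidence as the response

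*Combined protocol and SAP*

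**What the plan says.** Section 2.2 states the secondary hypotheses. Topiramate is expected to reduce positive alcohol expectancies, confidence in resisting heavy drinking, and nighttime drinking, in C-allele homozygotes but not in A-allele carriers. Expectancy and confidence are therefore outcomes of treatment there.

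The Aim 2 part of Section 7.2 describes a multilevel Poisson model whose response is the number of drinks taken after the early-evening report. On expectancy it says: "The day-level predictor of interest (i.e., expectation of positive effects of drinking) will also be included in the level-1 portion of the model". The predictor is then person-mean centred. The level-2 part "will include treatment group, binary factors for rs2832407 genotype (i.e., CC vs. A-carrier) and associated interaction terms". The person mean of expectancy is not listed at level 2. The paragraph closes: "This analysis will test the hypothesis that TOP will significantly reduce positive alcohol expectancies relative to PLA, but only in C-allele homozygotes", followed by "similar to the analysis of the primary outcome in Specific Aim 1".

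Other places also treat drinking as the response. The Study Summary gives the objective for the daily measures as "their interaction with genotype and medication group to predict nighttime drinking". Section 7.1 considers Aim 2 sample size for "moderation by the CC genotype of TOP's effects on the contingent relation between early evening outcome expectancies and nighttime drinking". Section 3.2.2 names multilevel models relating expectancies and self-efficacy (confidence) to daily drinking, varying by medication and genotype. Confidence does not appear in the Aim 2 text of Section 7.2. Section 6.3 shows that positive expectancy (three items) and confidence (to avoid drinking and to resist heavy drinking) are collected daily by interactive voice response (IVR).

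**The concern.** The hypothesis concerns a difference between arms in how high expectancy is. The model offered as its test has expectancy on the right-hand side, stripped of each subject's level. If the sentence is followed literally, an interaction on drinks or on the expectancy-drinking slope could be read as evidence that topiramate lowered expectancies when their level had not moved. Equally, a real fall in expectancies could go undetected. The alternative is that an expectancy model is built after the data are seen, with its items, distribution and contrast chosen then. The confidence hypothesis has no specified test at all.

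**Working it through.** **1. The model in symbols.** For subject i on day t, let Y be nighttime drinks, x positive expectancy, c_it = x_it − mean_i(x), M medication and G genotype. I take the associated interaction terms to include the cross-level ones, as the moderation question requires:

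log E(Y_it) = day-of-week + time + time² + daytime drinks + b0 + b1·M + b2·G + b3·MG + (g0 + g1·M + g2·G + g3·MG)·c_it + random effects

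This has 6 + 2 + 1 + 4 + 4 = 17 fixed effects, counting the intercept.

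**2. What each treatment term means.**
- b1 and b3: the medication effect on drinking, and its difference by genotype.
- g1 and g3: the medication effect on the within-person expectancy-drinking slope, and its difference by genotype.
- Effect of M, or of M by G, on x: no such term.

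The model can therefore address the nighttime-drinking hypothesis in Section 2.2 and the slope moderation in Section 7.1. Centring is suitable for the slope question.

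**3. Invariance.** Subtract a constant δ from every report of a topiramate C-allele homozygote:

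(x_it − δ) − (mean_i(x) − δ) = c_it

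With the drinks data held fixed, the design matrix and likelihood are identical, so every estimate and standard error is too. Numerical refits with δ = 0.5, 1 and 2 agreed to rounding error, both for a reduced eight-coefficient version and for all 17 terms. The medication contrast in mean expectancy among C-allele homozygotes moved by exactly 0.5, 1 and 2.

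**4. Limit of step 3.** The shift must be constant over the days that enter the person mean. Section 2.2 speaks of reduction across the weeks of the study, so the effect may build up. If the shift is δ·s_t, the centred value changes by −δ(s_t − mean s) and the fit changes. The coefficient on c is still a slope, not an effect on expectancy.

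**5. Illustration only.** The documents give no variances for expectancy, so the inputs marked *assumed* are mine.
- From the documents: 200 subjects in four comparable groups (50 each), 42 days, 20% missing.
- *Assumed*: expectancy SD 1, intraclass correlation (ICC) 0.3 to 0.7, and a 0.5 SD fall confined to topiramate C-allele homozygotes.

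With expectancy as the response, the variance of a subject mean is v = ICC + (1 − ICC)/(42 × 0.8). The SE of the medication-by-genotype interaction is √(4v/50), and of the contrast within C-allele homozygotes √(2v/50).

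| ICC | SE, interaction | Power | SE, CC contrast | Power |
|---|---|---|---|---|
| 0.3 | 0.160 | 88% | 0.113 | 99% |
| 0.5 | 0.203 | 69% | 0.144 | 94% |
| 0.7 | 0.238 | 56% | 0.168 | 84% |

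With 47 per group, the Section 7.1 figure for subjects still providing data, interaction power is 53% to 86%.

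For comparison, the written model was simulated (1,000 trials per setting, Poisson regression with subject-clustered SEs standing in for the mixed model). *Assumed*: ICC 0.5, mean nighttime drinks 0.5 to 4, random-intercept SD 0.7, within-person log-slope 0.30, random-slope SD 0.1 to 0.3.
- Same 0.5 SD fall: the slope interaction was significant in 4.5% to 7.5% of trials, close to its nominal 5%. The drinking interaction was significant in 4% to 8% if expectancy level does not drive drinking, and in 8% to 12% if it does (log-slope 0.3).
- No fall in expectancy, but a topiramate-CC slope of 0.10 instead of 0.30: the slope interaction was significant in 28% to 97% of trials, and the interaction in an expectancy-outcome model in 4% to 6%.

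**6. Confidence.** Section 2.2 makes it an outcome, Section 3.2.2 a correlate of drinking, and the Aim 2 text of Section 7.2 does not mention it. Section 2.2 also predicts that topiramate reduces both confidence and drinking, while the paragraph before links low confidence to heavier drinking. The two directions conflict.

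**The case against.** The best defence is that an expectancy-outcome model was intended. The closing reference to the Aim 1 analysis fits this: Aim 1 supplies medication, genotype, their interaction, time terms and random effects, and these could be applied to daily expectancy. Section 7.2 also speaks of models in the plural and follows the scheme of a cited daily-diary study. This makes the intention plausible, and a reader should not infer that no such analysis was meant. But the sentence refers to the model just described, and no text gives an expectancy model's distribution, item rule or contrast.

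A reader might also infer that confidence has no model anywhere. Section 3.2.2 does not support that, since it names multilevel models relating confidence to daily drinking. What is missing is a model with confidence as the response, and confidence in Section 7.2.

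Nothing in the documents says that a drinking or slope coefficient would be reported as a fall in expectancies. That is a risk of following the text literally, not a stated plan. It is also fair that the percentages rest on assumed inputs and add only scale to an algebraic point.

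**Conclusion.** The statement that this analysis tests a topiramate effect on expectancies is wrong as written. That follows from the roles of response and predictor and rests on no numerical assumption. The invariance result is exact for given drinks data and a shift constant over the days that enter the person mean; for a shift that builds up, the coefficient is still a slope. The power and rejection figures are illustrations.

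Two of the three Section 2.2 hypotheses, on expectancy and on confidence, therefore have no test written in these documents. The third, on nighttime drinking, does. It would be too strong to say that Aim 2 as a whole cannot be tested: the model serves the drinking and slope-moderation questions. Nor does the conflict over confidence make the hypotheses logically impossible; it is probably a drafting slip. The primary test is unaffected. This should be fixed, but it is a secondary-analysis matter.

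**What to change.** 1. Reword the last sentence of the Aim 2 methods in Section 7.2 so that the nighttime-drinking model tests effects on drinking and moderation of the expectancy-drinking slope only.
2. Add secondary mixed models with daily positive expectancy and daily confidence to resist heavy drinking as responses. Include medication, genotype, their interaction, day-of-week and time terms, and state how the three positive items are combined. Report the interaction and the medication contrast within each genotype, with confidence intervals, over the final six weeks. Define reduction as a between-arm difference, because IVR reporting starts with treatment and gives no daily baseline. The choice of distribution and link is the sponsor's.
3. Carry confidence into the Section 7.2 drinking model, to match Section 3.2.2.
4. Reconcile the predicted direction for confidence within Section 2.2 before unblinding.

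The cost is some rewording and two extra secondary models on data already collected. Data collection and the primary analysis do not change.
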